4.2 Reference Start Date, Study Day, and Period Day

Study Day will be calculated as follows and will be used to show start/end day of assessments or events:

Study Day = (Date of event – Date of first dose) + 1 if date of event is on or after the date of first dose of study treatment

= (Date of event – Date of first dose) if date of event is before the date of first dose of study treatment.

Period Day will be calculated as follows for each study period separately:

Period Day for DB Treatment Period = (Date of event – Date of first dose of study treatment during the DB Treatment Period) + 1 if date of event is on or after the date of first dose of study treatment during the DB Treatment Period

= (Date of event – Date of first dose of study treatment during the DB Treatment Period) if date of event is before the date of first dose of study treatment during the DB Treatment Period

Period Day for OLE Period = (Date of event – Date of first dose of study treatment during the OLE Period) + 1.

In the situation where the date of event is partially or completely missing, the Study Day and corresponding Period Day will be missing.

4.3 Windowing Conventions

When available, visits will be analyzed as scheduled (refer to protocol Appendices 1 and 2). ET and/or unscheduled/retest measurements will only be included if a scheduled measurement is not available, and the ET or unscheduled/retest measurement falls within the analysis visit windows as described in [Table 1](#).

If there is more than one retest, unscheduled or ET assessment for a given analysis visit, the assessment closest to the target day will be retained for data summary of that visit; if there are 2

observations with equal distance to the target day, then the later one will be retained. All data from scheduled, retest, unscheduled, and ET visit assessments will be listed.

Table 1: Analysis Visit Windows

Analysis Visit	Target Study Day	Visit Window (Period Day)
DB Treatment Period		
DB Baseline	1	Refer to DB Treatment Period Baseline definition in Section 4.1
Week 1 (Cohort 2 only)	Day 8	Post first dose – Day 11
Week 2	Day 15	Cohort 1: Post first dose – Day 21 Cohort 2: Day 12 – Day 21
Week 4	Day 29	Day 22 – Day 42
Week 8	Day 57	Day 43 – Day 70
Week 12	Day 85	Day 71 – Day 98
Week 16	Day 113	Day 99 – Day 126
Week 20	Day 141	Day 127– Day 154
Week 24*	Day 169	Day 155 – (Last treatment day + 6) in DB period for subjects never treated in OLE; Day 155 – Pre first dose in OLE for subjects treated in OLE
OLE Period **		
OLE Baseline	OLE Day 1	Refer to OLE Period Baseline definition in Section 4.1
Week 25	OLE Day 8	Post first dose in OLE – OLE Day 18
Week 28	OLE Day 29	OLE Day 19 – OLE Day 56
Week 36	OLE Day 85	OLE Day 57 – OLE Day 112
Week 44	OLE Day 141	OLE Day 113 – OLE Day 168
Week 52	OLE Day 197	OLE Day 169 – (Last treatment day + 6)
Safety Follow-up 1	Last treatment day + 14 days (± 3 days)	(Last treatment day + 7) – (Last treatment day + 21 days)
Safety Follow-up 2	Last treatment day + 28 days (± 3 days)	(Last treatment day + 22 days) - (Last contact day)

DB = Double-Blind; OLE = Open-Label Extension; SFU = Safety Follow-Up

* Week 24 is the last scheduled visit in DB Treatment Period and first scheduled visit in OLE Period.

** The days are Period Day (refer to Section 4.2) in the OLE Period.

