10.5.7.6. Pulmonary Function Monitoring

Based on changes in pulmonary function observed with the use of S1P receptor modulators fingolimod and siponimod, approved for relapsing multiple sclerosis ([GILENYA 2010](#), [MAYZENT 2019](#)), pulmonary function will be assessed in this study at Screening, Week 12, Week 24, Week 52, and ET if applicable ([Appendix 1](#) and [Appendix 2](#)).

Subjects experiencing clinically significant dyspnea or other respiratory AEs may need to have additional PFT testing as clinically indicated. Severity of respiratory AEs should be categorized using the CTCAE scale described in [Appendix 4](#). Investigators should consider interruption of study drug when there is a clinically significant respiratory AE considered related to study drug that leads to limitations in instrumental or self-care activities of daily living. The decision to interrupt study drug should be discussed with the Medical Monitor. Subjects should be promptly referred to a pulmonologist for further evaluation and treatment. The pulmonologist should be provided with a standard referral letter explaining the reason for the referral along with information about the investigational drug. Clinically significant respiratory AEs should be followed until there is stability, improvement, or resolution.

Re-initiation of study drug can only be considered if the respiratory AE has improved, stabilized, and/or resolved, the individual risk-benefit is favorable (as determined by the Investigator, in agreement with the pulmonologist) and after discussion with the Medical Monitor.

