4.5 Handling of Retests, Unscheduled Visits, and Early Termination Data

Retests measurements, unscheduled measurements, and ET visit assessments will be included in analysis and summarized via analysis visit windowing according to the windowing conventions in Section 4.3.

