10.4 Other Efficacy Endpoints

The following other efficacy endpoints will also be summarized and analyzed:

- Proportion of subjects achieving a SALT I score ≤ 10 over time
- Proportion of subjects achieving a SALT I score ≤ 20 over time

- Proportion of subjects achieving a $\geq 90\%$ improvement from Baseline in SALT I over time
- Change from Baseline in AASIS at Week 12
- Change from Baseline in AA-QLI at Week 12
- Percent change from Baseline in peripheral lymphocyte counts at Weeks 1 (Cohort 2 only), 2, 4, 8, 12, 16, and 20

Other efficacy endpoints will be summarized and analyzed as for the proportion-based exploratory efficacy endpoints or continuous exploratory efficacy endpoints, as applicable, for visits occurring during the DB Treatment Period (refer to Section 10.3).

No sensitivity analyses and no subgroup analyses will be performed for the other efficacy endpoints.

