11.6 Pulmonary Function Test

Pulmonary function tests (PFTs) will be performed according to the Schedules of Assessments (refer to Appendix 1 and Appendix 2 in the protocol) and include forced expiratory volume at 1 second (FEV₁), forced vital capacity (FVC), and forced expiratory flow at 25 to 75% (FEF 25-75) measurements. Where locally available, diffusing capacity of the lungs for carbon monoxide (DLCO) measurements will also be performed.

The observed values and change from baseline values in each of the following PFT measurements will be summarized using descriptive statistics by visit:

- FEV₁ (L)
- % Predicted FEV₁
- FVC (L)
- % Predicted FVC
- FEV₁/FVC ratio
- % Predicted FEV₁/FVC ratio
- FEF 25-75 (L/sec)
- % Predicted FEF 25-75
- Total Lung Capacity (TLC; L)
- % Predicted TLC
- DLCO (mL/min/mmHg)
- % Predicted DLCO

Frequency count and percentage of subjects with markedly abnormal values will be reported by visit as well as at any time after baseline for each of the following predefined markedly abnormal criteria separately:

- % Predicted FEV₁ < 50%
- % Predicted FVC < 50%
- % Predicted FEV₁/FVC ratio < 50%

Incidence of subjects with potentially important PFT abnormal measurements will also be identified using the criteria below and summarized similarly:

- Decrease from DB baseline > 20% in FEV₁, i.e., percent change from DB baseline < -20%
- Decrease from DB baseline > 20% in FVC, i.e., percent change from DB baseline < -20%
- Decrease from DB baseline > 20% in DLCO, i.e., percent change from DB baseline < -20%

Shift tables from baseline to each scheduled post-baseline in Investigators' overall interpretation of the PFT (normal, abnormal NCS or abnormal CS) will be provided as well. Only subjects with a baseline result and a result at the specified post-baseline visit will be considered.

All PFT results and overall interpretation of PFTs will be listed and markedly, potentially important abnormal values will be flagged.

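### SAP Table 1's single visit grid sends most early-termination lung and eye results to visits where those tests are not scheduled, so they miss the PFT shift table and the Week 12, 24 and 52 summaries

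*SAP*

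**What the plan says.** Table 1 in SAP 4.3 is the only set of analysis windows. For ET data the section says "ET and/or unscheduled/retest measurements will only be included if a scheduled measurement is not available", and the value must also fall inside a Table 1 window. SAP 4.5 applies this generally: "Retests measurements, unscheduled measurements, and ET visit assessments will be included in analysis and summarized via analysis visit windowing".

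The double-blind rows are Week 1 (Cohort 2 only) and Weeks 2, 4, 8, 12, 16, 20 and 24. The Week 24 row reads "Day 155 – (Last treatment day + 6) in DB period for subjects never treated in OLE". The open-label extension (OLE) rows are Weeks 25, 28, 36, 44 and 52. Week 36 covers "OLE Day 57 – OLE Day 112", and Week 52 starts at OLE Day 169. These are the SALT I and laboratory visits in Protocol Appendices 1 and 2.

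The lung and eye tests follow a sparser schedule. Protocol 10.5.7.6 says "pulmonary function will be assessed in this study at Screening, Week 12, Week 24, Week 52, and ET if applicable", and 10.5.7.7 gives the same times for ophthalmic testing. The questionnaires (AASIS, AA-QLI) are taken at Day 1, Weeks 12, 24, 36 and 52/ET, and SFU 2.

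SAP 11.6 summarises PFT values by visit and counts marked abnormalities both by visit and at any time. For the investigator's overall PFT interpretation it plans "Shift tables from baseline to each scheduled post-baseline in" that interpretation, using subjects with a result at the visit. SAP 11.7 reports ophthalmic exam categories by visit only, and marked foveal-thickness increases by visit and at any time.

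For the questionnaires, SAP 10.3 names Week 24 and 10.4 adds "Change from Baseline in AASIS at Week 12". Both reach the SALT I repeated-measures model of 10.1 by cross-reference.

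**The concern.** The protocol measures lung function and the macula because of effects seen with other drugs of the class, and it asks for these tests at ET. For a subject who stops, the ET test is the last result close to treatment. If most such results are assigned to visits where nobody else is tested, the Week 12, 24 and 52 columns describe mainly the subjects who continued. The shift table is the only summary of the investigator's overall PFT reading, and it has no any-time row to catch the rest.

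The questionnaires raise a related question. They are scheduled twice after baseline in the double-blind period, but they inherit a model with eight visits. The SAP does not say which visits enter, so the place of an ET questionnaire is undefined.

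**Working it through.** **Inputs**
- Target days, SAP Table 1: double-blind 8, 15, 29, 57, 85, 113, 141, 169; OLE 8, 29, 85, 141, 197.
- Test schedules: Protocol 10.5.7.6, 10.5.7.7, Appendices 1 and 2.
- ET visit within one week of the last dose: Protocol 9.5.
- Drop-out 15% over 24 weeks; 42 subjects in Cohort 2, 78 in all: SAP 3.2.
- Drop-out timing: not given. Every timing below is an assumption.

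**The plan's own figures.** Each Table 1 window starts at the midpoint of neighbouring target days, rounded up. Double-blind: (8+15)/2 = 11.5, so 12; (15+29)/2 = 22; then 43, 71, 99, 127 and 155. OLE: (8+29)/2 = 18.5, so 19; then 57, 113 and 169. All match the printed table. The sample size also reproduces: 35/0.85 = 41.2, so 42.

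**Step 1. Double-blind ET days (Day 2 to 168)**

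| ET day | Assigned visit | PFT, eye or questionnaire scheduled? | Days |
|---|---|---|---|
| 2–70 | Week 1, 2, 4 or 8 | No | 69 |
| 71–98 | Week 12 | Yes | 28 |
| 99–154 | Week 16 or 20 | No | 56 |
| 155–168 | Week 24 | Yes | 14 |

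Off-schedule: (69+56)/167 = 125/167 = 74.9%. If ET can fall up to a week later (Day 175), 125/174 = 71.8%. If the Week 12 visit took place on Day 85, an ET value on Days 85–98 (14 days) gives way to it, so (125+14)/167 = 83.2% would not fill a Week 12 or 24 slot.

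**Step 2. OLE ET days (OLE Day 2 to 196)**
- PFT and eye: only Week 52 is scheduled, so Days 2–168 are off-schedule: 167/195 = 85.6% (167/202 = 82.7% if extended a week).
- Questionnaires: Weeks 36 and 52 are scheduled, so 195 − 56 − 28 = 111 days are off-schedule: 111/195 = 56.9%.

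**Step 3. Where an off-schedule ET value goes**

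| Output | Off-schedule ET value |
|---|---|
| PFT interpretation shift | Left out |
| PFT and OCT by-visit summaries | Not in Week 12/24/52; at most a near-empty row elsewhere |
| Ophthalmic exam categories | Same, with no any-time count |
| Marked PFT and foveal-thickness counts, any time | Included |
| Listings | Included |

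**Step 4. Subjects.** Expected double-blind drop-outs: 0.15 × 42 = 6.3, or 0.15 × 78 = 11.7 if the rate is extended to Cohort 1. With evenly spread ET days, 72% to 75% off-schedule gives 4.5 to 4.7, or 8.4 to 8.8. Simulated timings give 74% (constant hazard), 82% (front-loaded) and 64% (back-loaded). The last two give 6.3 × 0.64 = 4.0 to 6.3 × 0.82 = 5.2, or 11.7 × 0.64 = 7.5 to 11.7 × 0.82 = 9.6.

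**Step 5. Questionnaire model.** The inherited visit factor has eight levels (Weeks 1 to 24), so an unstructured covariance has 8 × 9/2 = 36 parameters. Six of those visits would hold only windowed ET values, and 36 parameters are unlikely to be estimable. With Weeks 12 and 24 alone there are 2 × 3/2 = 3. The text supports either reading.

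**The case against.** The strongest reply is that little is lost. Nothing in SAP 11.6 or 11.7 suppresses a Week 8 or Week 16 row, and 4.5 says ET data are included. Marked PFT changes and foveal-thickness increases are counted at any time. Adverse events leading to discontinuation are summarised and listed, and every ET value is listed. Subjects who stop drug are asked to continue visits (Protocol 8.1, 9.5), so some will supply scheduled values. Those stopping on Days 99–154 should already have a Week 12 value. The numbers are small, and the SALT I analyses are untouched.

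All of this stands, and it limits the point. Three stronger readings fail for these reasons:
- A reader might infer that early ET lung and eye results have no planned analysis. The any-time counts, by-visit rows and listings show otherwise.
- A reader might infer that ET questionnaires drop out of the model and that early stoppers never enter it. No passage limits that model to Weeks 12 and 24; read literally, 10.1 would keep them. The fault is an unstated visit list. In the OLE there is no questionnaire model, only descriptive summaries.
- A reader might suppose that early stoppers stopped for lung, eye or quality-of-life reasons. The documents give no distribution of reasons.

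The reply does not cover the PFT interpretation shift and the ophthalmic exam categories, which have no any-time row. Nor does it cover the Week 12, 24 and 52 columns. A later scheduled value from a subject who stayed on study reflects time off drug and does not replace the ET result.

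**Conclusion.** The point holds for the lung and eye tables. Table 1 assigns 75% of possible double-blind ET days and 86% of OLE ET days to visits where neither test is scheduled. The double-blind share stays between 64% and 82% under the timings tried. Roughly 4 to 9 double-blind subjects are involved, just under 10 at the front-loaded extreme, and fewer if subjects stay for scheduled visits. That count assumes the 15% drop-out and a drop-out pattern that the documents do not supply; the upper end also extends the rate from Cohort 2 to all 78 subjects. Omission from the shift table rests on the natural reading that a scheduled visit there means one where PFT is scheduled.

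This is a gap in descriptive safety reporting, not a loss of marked signals. For the questionnaires, the finding is only that the model's visits must be stated.

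**What to change.** Keep Table 1. Add one labelled row, last on-treatment value (Week 24/ET for the double-blind period, Week 52/ET for the OLE), to the PFT summary, the PFT interpretation shift, the OCT table and the ophthalmic exam table. Define how long after the last dose a value still counts. Table 1 closes its Week 24 (subjects never treated in the OLE) and Week 52 windows at the last treatment day plus 6, whereas the protocol allows the ET visit within a week and these tests up to 10 days either side of most visits.

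Do not widen the windows so that early ET values carry a Week 12, 24 or 52 label. Midpoints from the sparse schedule, (85+169)/2 = 127 in the double-blind period, would remove every off-schedule day, but they would call a Day 2 result Week 12 and, with a single OLE window, an OLE Day 2 result Week 52.

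In SAP 10.3 and 10.4, state that the AASIS and AA-QLI model uses Weeks 12 and 24, and summarise ET questionnaire values in a separate ET row.

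The cost is a few lines of SAP text and some programming, with no new data. The drawback is that the added row pools different lengths of exposure, which its label makes visible.

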4.4 Descriptive Statistics

All continuous variables will be summarized by presenting the number of subjects, mean, SD, median, minimum, and maximum. Categorical variables will be summarized using frequencies and percentages. Summary tables will be presented by treatment and visit, when applicable.

4.5 Handling of Retests, Unscheduled Visits, and Early Termination Data

Retests measurements, unscheduled measurements, and ET visit assessments will be included in analysis and summarized via analysis visit windowing according to the windowing conventions in Section 4.3.

4.6 Software Version

All analyses will be performed using SAS[®] software Version 9.4.

5 STATISTICAL CONSIDERATIONS

5.1 Analysis Sets

The following analysis sets will be defined for the DB Treatment Period and OLE Period separately:

Table 2. Summary of Analysis Sets

Analysis Set	Description
DB Treatment Period	
Randomized Set	
The Randomized Set includes all randomized subjects, irrespective of whether they received any study drug.
 
All subjects will be analyzed according to the treatment group to which they were randomized.

Full Analysis Set (FAS)	
The FAS includes all randomized subjects with a SALT I < 95 at Baseline who received at least one dose of study drug. The FAS will be used for the primary analysis of the primary efficacy endpoint and main analysis of the secondary, exploratory, and other efficacy endpoints.
 
All subjects will be analyzed according to the treatment group to which they were randomized.

Modified Full Analysis Set (mFAS)	
The mFAS consists of all randomized subjects with a SALT I < 95 at Baseline who received at least 1 dose of study drug, have a Baseline measurement, and have at least 1 post-randomization measurement.
 
The mFAS is endpoint specific, therefore subjects included in the analysis set for 1 endpoint may differ from another endpoint, based on the Baseline and post-Baseline data. The mFAS will be used for sensitivity analyses for the primary and secondary endpoints in SALT I.
 
All subjects will be analyzed according to the treatment group to which they were randomized.

Analysis Set	Description
Per Protocol Set (PPS)	
The PPS consists of all subjects in the FAS with no major protocol deviations (PD) potentially having an impact on the SALT I-related primary and secondary efficacy endpoints (refer to Sections 7.2 and 10.1).
 
The PPS will be used for sensitivity analyses for the primary and secondary efficacy endpoints in SALT I to evaluate the influence of major PD potentially having an impact on the efficacy endpoints.
 
All subjects will be analyzed according to the treatment group to which they were randomized.

Safety Set (SAF)	
The SAF consists of all randomized subjects who received at least 1 dose of study drug.
 
All safety analysis in the DB Treatment Period will be performed using SAF. All subjects will be analyzed according to the actual treatment they received. In case a subject received more than one actual treatment, the first treatment received will be used for the safety analysis.

OLE Period	
OLE Safety Set (OLE SAF)	
The OLE SAF includes all subjects who received at least one dose of study drug in the OLE Period.
 
All safety analysis in the OLE Period will be performed using OLE SAF. All subjects will be analyzed according to the actual treatment they received. In case a subject received more than one actual treatment, the first treatment received will be used for the safety analysis.

OLE Full Analysis Set (OLE FAS)	
The OLE FAS includes all subjects with a SALT I < 95 at Baseline who received at least one dose of study drug in the OLE Period.
 
All efficacy analysis in the OLE Period will be performed using OLE FAS. All subjects will be analyzed according to the actual treatment they received. In case a subject received more than one actual treatments, the first treatment received will be used.

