Cohort 2: All subjects (approximately 42 subjects) enrolled under protocol Amendments 2.0 and 2.1. Subjects will be randomized in a 4:1:2 ratio to receive etrasimod 3 mg, etrasimod 2 mg, or placebo orally, once daily, in a double-blind manner for the 24-week DB Treatment Period. Randomization will be stratified by SALT I score (< 50 , ≥ 50) at Day 1/Baseline. During the DB Treatment Period, subjects assigned to etrasimod 3 mg will receive etrasimod 2 mg orally, once daily from Day 1 to the Week 1 visit and will transition at the Week 1 visit to etrasimod 3 mg orally, once daily for the remainder of the DB Treatment Period. During the OLE Period, all subjects will receive etrasimod 2 mg orally, once daily from the Week 24 visit to the Week 25 visit. At the Week 25 visit all subjects will transition to 3 mg orally, once daily for the remainder of the OLE Period.

Figure 1: Schematic Diagram of Study Design

^a Randomized 2:1 (etrasimod 2 mg:placebo) in the Double-Blind Treatment Period.

^b Subjects entering the Open-Label Extension Period (Week 24 visit) before implementation of Amendments 2.0 and 2.1 will transition to 3 mg once daily at their next study visit (refer to Section 10.5.7.5 and Appendix 1 of the protocol for additional information on Holter monitoring). Subjects entering the Open-Label Extension Period (Week 24 visit) after implementation of Amendments 2.0 and 2.1 will receive etrasimod 2 mg from the Week 24 visit to the Week 25 visit and will transition to etrasimod 3 mg at the Week 25 visit. Of note, subjects already in the Open-Label Extension Period at the time of Amendments 2.0 and 2.1 implementation may be allowed to continue on etrasimod 2 mg at the Investigator’s discretion provided that they have achieved a SALT I score ≤ 20 .

^c SFU 1 and SFU 2 are to be conducted 2 and 4 weeks (± 3 days) after last dose of study drug, respectively.

^d Randomized 4:1:2 (etrasimod 3 mg:etrasimod 2 mg:placebo) in the Double-Blind Treatment Period.

* Subjects will initiate treatment on 2 mg etrasimod for 1 week prior to starting 3 mg.

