3.3 Treatment Randomization and Unblinding Procedures

Under protocol amendments 1.0 and 1.1 (Cohort 1), randomization will take place at the Day 1 visit prior to first dosing. Subjects who complete all Screening requirements and remain eligible for the study will be randomized in a 2:1 ratio to receive etrasimod 2 mg or placebo orally once daily for 24 weeks in the DB Treatment Period. The randomization will be stratified by SALT I score (< 100, 100) at Day 1/Baseline.

Subjects enrolled during Amendment 2.0 and later (Cohort 2) who complete all Screening requirements and remain eligible for the study will be randomized in a 4:1:2 ratio to receive etrasimod 3 mg, etrasimod 2 mg, or placebo orally once daily for 24 weeks in the Double-Blind Treatment Period.

This study includes a DB Treatment Period with limited access to the randomization code. The Unblinding Plan documents the procedure for unblinding.

After completing the 24-week DB Treatment Period, eligibility for participation in the OLE Period will be determined. All eligible subjects in Cohort 1 will receive etrasimod 2 mg orally, for at least 1 week during the OLE Period. Subjects in Cohort 1 will transition to 3 mg at the Week 25 visit or at their next OLE study visit after the implementation of Amendments 2.0 and 2.1. Subjects in Cohort 2 will receive etrasimod 2 mg orally, once daily for 1 week during the OLE Period and then transition to etrasimod 3 mg orally, once daily for the remainder of the OLE Period. Subjects from Cohort 1 who are already in the OLE Period at the time of Amendments 2.0 and 2.1 implementation may be allowed to continue on etrasimod 2 mg at the Investigator's discretion provided that they have achieved a SALT I score ≤ 20 .

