9 STUDY TREATMENT EXPOSURE AND TREATMENT COMPLIANCE

Duration of exposure to study drug, in days, will be computed overall and for each study period as follows:

Overall duration of exposure = (Date of last dose of study drug, regardless of the study period –
Date of first dose of study drug during the DB Treatment Period)
+ 1

Duration of exposure for DB Treatment Period = (Date of last dose of study drug during the DB Treatment Period – Date of first dose of study drug during the DB Treatment Period) + 1

Duration of exposure for OLE Period = (Date of last dose of study drug during the OLE Period – Date of first dose of study drug during the OLE Period) + 1

Duration of exposure to etrasimod 2 mg and etrasimod 3 mg will also be computed overall and for the OLE Period as follows:

Overall duration of exposure to etrasimod 2 mg = (Date of last dose of etrasimod 2 mg, regardless of the study period – Date of first dose of etrasimod 2 mg, regardless of the study period) + 1

Overall duration of exposure to etrasimod 3mg = (Date of last dose of etrasimod 3 mg, regardless of the study period – Date of first dose of etrasimod 3mg, regardless of the study period) + 1

Duration of exposure to etrasimod 2 mg during the OLE Period = (Date of last dose of etrasimod 2 mg during the OLE Period – Date of first dose of etrasimod 2 mg during the OLE Period) + 1

Duration of exposure to etrasimod 3mg during the OLE Period = (Date of last dose of etrasimod 3 mg during the OLE Period – Date of first dose of etrasimod 3mg during the OLE Period) + 1

In addition, duration of dose interruptions (in days) will be calculated overall and by study period as follows:

Overall duration of dose interruptions =

$$\sum_{i=1}^n (\text{End date of dose interruption } i - \text{Start date of dose interruption } i) + 1$$

if subject has at least one dose interruption interval

0 if subject has no dose interruption intervals

where n = total number of dose interruption intervals during the whole study.

Duration of dose interruptions for the DB Treatment Period and OLE Period will be calculated similarly, but n will be the total number of dose interruptions during the DB Treatment Period and total number of dose interruptions during the OLE Period, respectively.

Compliance with study drug, in percentage, will be calculated overall and by study period as follows:

Compliance with study drug (%) for DB Treatment Period=

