10.5 Exploratory Efficacy Endpoints during the Open-Label Extension Period

The following efficacy endpoints will be assessed at scheduled visits during the OLE Period up to 52 weeks:

- Change and percent change from Baseline in SALT I over time
- Change from Baseline in AASIS over time
- Change from Baseline in AA-QLI over time
- Change from Baseline in peripheral lymphocyte counts over time
- Proportion of subjects achieving a $\geq 30\%$ improvement from Baseline in SALT I over time
- Proportion of subjects achieving a $\geq 50\%$ improvement from Baseline in SALT I over time
- Proportion of subjects achieving a $\geq 75\%$ improvement from Baseline in SALT I over time
- Proportion of subjects achieving a $\geq 90\%$ improvement from Baseline in SALT I over time
- Proportion of subjects achieving a SALT I score ≤ 10 over time
- Proportion of subjects achieving a SALT I score ≤ 20 over time

These endpoints will be summarized by visit using descriptive statistics based on the OLE FAS, with following considerations:

- Missing data will not be imputed

- Summaries will be provided for the three treatment groups in the OLE Period (OLE 2mg, OLE 2mg/3mg, OLE 3mg) and three randomized treatment groups in the DB Treatment Period (DB 2mg, DB 3mg, DB placebo)
- Change and percent change from baseline in continuous variables will be summarized using change from OLE Baseline and DB Baseline (refer to Section 4.1).

The photographic assessments of the full scalp for all subjects, of the eyebrows and eyelashes for subjects who have hair loss in these areas at Day 1/Baseline, and of the fingernails for subjects with fingernail changes related to AA (eg, pitting, white spots, and roughness) at Day 1/Baseline, will be reported in listing.

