11 SAFETY ANALYSIS

Unless otherwise indicated, safety data will be summarized overall and by treatment group and visit, when applicable, for each study period separately, based on the SAF for the DB Treatment Period and OLE SAF for the OLE Period.

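### SAP Table 2 labels open-label subjects by first treatment received without reconciling this with the three OLE groups; Section 11.8 names a different safety set from the rest of the plan; and the Appendix 1 group notes leave gaps and overlaps

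*SAP*

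**What the plan says.** **Labelling rule.** SAP Section 5.1, Table 2, analyses the OLE Safety Set (OLE SAF) by actual treatment and adds: "In case a subject received more than one actual treatment, the first treatment received will be used for the safety analysis". The OLE FAS entry has the same rule: "In case a subject received more than one actual treatments, the first treatment received will be used".

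**Starting dose.** For Cohort 1, Section 3.3 states: "All eligible subjects in Cohort 1 will receive etrasimod 2 mg orally, for at least 1 week during the OLE Period". For Cohort 2, Section 3.1 states: "During the OLE Period, all subjects will receive etrasimod 2 mg orally, once daily from the Week 24 visit to the Week 25 visit".

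**Reported groups.** Sections 10.5 and 11.8 call for three OLE groups: 2 mg, 2 mg/3 mg and 3 mg. Appendix 1 defines them in three notes:
- 2 mg: Cohort 1 subjects who completed or discontinued the OLE before Amendments 2.0/2.1 were implemented, and subjects of either cohort who discontinued before moving to 3 mg.
- 2–3 mg: Cohort 1 subjects who took 2 mg and later moved to 3 mg.
- 3 mg: Cohort 1 subjects who took 2 mg for one week and then 3 mg, and Cohort 2 subjects.

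**Safety population.** Table 2 states: "All safety analysis in the OLE Period will be performed using OLE SAF". Section 11 sets the default as "based on the SAF for the DB Treatment Period and OLE SAF for the OLE Period". Section 11.8, in its list of exceptions, names the OLE FAS instead, which is restricted to Baseline SALT I below 95.

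**The concern.** Long-term safety and efficacy of 2 mg and 3 mg is a secondary objective (SAP 2.1.2). In the OLE tables, the column is how a reader connects an adverse event, a liver or lymphocyte abnormality, or a lung or eye finding with a dose. If a programmer applies Table 2 literally, events that occur on 3 mg are counted under 2 mg. If a programmer applies Section 11.8 literally, some treated subjects disappear from open-label safety altogether. If the Appendix 1 notes are applied literally, some subjects have no OLE column and others have two. Three OLE efficacy tables that use these groups (the Week 36 versions of 14.2.8, 14.2.9 and 14.2.13) are already due in Batch 1 of the primary analysis.

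**Working it through.** The plan gives no figure of its own on this point, so the check sets the passages side by side.

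**1. Both rules applied to the permitted dosing paths.** The documents allow at least these 11 paths through the OLE. The amendment means implementation of Amendments 2.0/2.1; C1 and C2 are the cohorts.

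| Path | Table 2, literal | Appendix 1 notes |
|---|---|---|
| C1, completed before amendment | 2 mg | 2 mg |
| C1, discontinued before amendment | 2 mg | 2 mg |
| C1, in OLE at amendment, more than one week of 2 mg, then 3 mg | 2 mg | 2–3 mg |
| C1, in OLE at amendment, kept on 2 mg at SALT I ≤ 20, completes | 2 mg | none |
| Same, but discontinues | 2 mg | 2 mg |
| C1, past Week 44 at amendment, completes | 2 mg | none |
| C1, enters after amendment, one week of 2 mg, then 3 mg | 2 mg | 2–3 mg and 3 mg |
| C1, enters after amendment, stops in first week | 2 mg | 2 mg |
| C1, enters after amendment, kept on 2 mg after a lymphocyte interruption before any 3 mg dose, completes | 2 mg | none |
| C2, one week of 2 mg, then 3 mg | 2 mg | 3 mg |
| C2, stops before 3 mg | 2 mg | 2 mg and 3 mg |

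Table 2 read literally labels 11 of 11 paths 2 mg, so two of the three columns are empty. The Appendix 1 notes leave 3 of 11 paths with no column and put 2 of 11 in two columns.

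The past-Week-44 path arises because the switch to 3 mg happens at the next visit (SAP 3.1). That visit is Week 52, where no drug is given (Protocol 6.3, Table 2, note d). The lymphocyte path rests on Protocol 10.5.7.2, which Protocol 8.1 contradicts (see the fix).

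**2. Exposure that a literal 2 mg label would hide.** SAP 4.3, Table 1, puts Week 52 at OLE Day 197, and no dose is given there, so planned dosing covers OLE Days 1 to 196. Days on 3 mg = 197 − switch day.
- Week 25 (Day 8): 197 − 8 = 189; 189/196 = 96%
- Week 28 (Day 29): 197 − 29 = 168; 168/196 = 86%
- Week 36 (Day 85): 197 − 85 = 112; 112/196 = 57%
- Week 44 (Day 141): 197 − 141 = 56; 56/196 = 29%

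**3. OLE safety population.** The OLE FAS is named only in Section 11.8. The OLE Safety Set is named in Table 2, in Section 11, in Table 4 (Section 12) and in Protocol 11.10. The OLE safety tables in Appendix 3 number 8 adverse event + 10 laboratory + 1 vital signs + 2 ECG + 3 pulmonary + 3 eye = 27, and all 27 titles carry the OLE Safety Set. The six OLE efficacy tables (14.2.8 to 14.2.13) all carry the OLE FAS, so 27 + 6 = 33 outcome tables depend on the grouping.

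**4. Who would be dropped.** Protocol 10.3.1 gives entry at SALT I ≥ 50 for Cohort 1, and ≥ 25 and < 95 for Cohort 2. By these criteria, subjects at 95 or above can come only from Cohort 1. Their number is not stated. If they were 10%, 25% or 50% of the 36 planned (assumption), that is 3.6, 9 or 18 subjects before dropout.

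**The case against.** **On the label.** A reader might infer that the first-treatment rule makes the 2–3 mg column impossible to fill. The documents do not support that. Appendix 1 names the 2–3 mg sequence as an OLE treatment group, and its 3 mg note counts subjects with a one-week 2 mg lead-in as 3 mg. If treatment in Table 2 means the planned sequence of Appendix 1, all three columns can be filled. What remains is that Table 2 neither says this nor refers to Appendix 1, and that Section 9 treats the doses as separate exposures: "Duration of exposure to etrasimod 2 mg and etrasimod 3 mg will also be computed overall and for the OLE Period as follows". The same sentence governs the double-blind Safety Set, where the 3 mg arm takes 2 mg in its first week, so the clarification belongs there too.

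**On the safety set.** Section 11 allows exceptions and Section 11.8 lists the OLE FAS as one, so it might be read as deliberate. That is hard to sustain: the Table 4 entry that introduces the OLE FAS says safety stays on the OLE Safety Set. The weight of the other passages makes a slip likely and the practical risk small, but Section 11.8 is where a programmer would look.

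**On importance.** Protocol 11.10 foresees one OLE group plus the double-blind subgroups, and Appendix 1 provides those Total and double-blind-group columns. The labelling problems do not touch them. The OLE analyses are descriptive, and the number of subjects without a column may be small or zero. The table shells are a separate document (SAP Section 4) and may already resolve some of this. All of that stands, and it limits the point to a correction of wording.

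**Conclusion.** Three conflicts in the SAP text hold.

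1. The first-treatment sentence, read literally, contradicts the three OLE groups. A sequence reading would reconcile them but is not written down.
2. Section 11.8 conflicts with every other statement of the OLE safety population. Followed as written, it excludes treated Cohort 1 subjects with Baseline SALT I ≥ 95 from every column, including Total.
3. The Appendix 1 notes are neither exhaustive nor exclusive: Cohort 1 subjects who complete on 2 mg only after the amendment have no OLE column, and two paths fit two columns.

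Items 1 and 3 affect only the descriptive OLE dose columns. Double-blind results and power do not change. The documents do not show that outputs will in fact be mislabelled or subjects in fact dropped; they show that the text permits it. The numbers affected are not stated, and the 3.6, 9 and 18 above rest on assumed shares. This should be corrected before the OLE tables are programmed.

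**What to change.** Change analysis labels only; dosing is untouched.

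- **(a) Table 2, OLE SAF and OLE FAS:** replace the first-treatment sentence with a reference to the Appendix 1 OLE groups.
- **(b) Appendix 1:** define the groups by dose sequence.
  - OLE 2 mg: no 3 mg dose taken in the OLE, for any reason.
  - OLE 3 mg: at least one 3 mg dose, and either Cohort 2, or Cohort 1 with the transition scheduled at the Week 25 visit, whatever the calendar date of OLE entry.
  - OLE 2–3 mg: all other subjects with at least one 3 mg dose, that is, Cohort 1 with the transition scheduled after Week 25.

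  Applied to the 11 paths above, this gives 8 in 2 mg, 2 in 3 mg and 1 in 2–3 mg, with none unassigned or doubled (8 + 2 + 1 = 11).
- **(c) Section 11.8:** change OLE FAS to OLE SAF.
- **(d) Double-blind Safety Set:** state that the 3 mg treatment includes its 2 mg first week. Check the separate table shells against all of these definitions.

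Protocol 8.1 and 10.5.7.2 differ on what follows a confirmed lymphocyte count below 0.2 × 10⁹ cells/L, and the sponsor must reconcile them. The groups in (b) work under either text.

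The cost is a few sentences in the SAP and a check of the shells. The Appendix 3 safety titles already name the OLE Safety Set and need no change.
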